Evidence suggests that there may be a significant cerebral vascular component to cognitive impairment associated with AD and therefore, treatments targeting cerebral perfusion and vascular health are worth pursuing (Paillard, 2015). External counterpulsation (ECP) treatment improves coronary and peripheral vascular health and may improve cerebral vascular health. Physical exercise is the most basic and efficient way to improve blood flow (Erickson, Voss, et al., 2011) and has been shown to increase cardiac output, which in turn leads to an increase in CBF (Paillard, 2015). Wang, Karp, et al. (2002) and Verghese, Lipton, et al. (2003) have shown that elderly patients who partake in physical activity are less likely to develop dementia and experience cognitive decline. However, due to cognitive or physical decline, patients with signs of dementia are not always able to exercise. Renew™ NCP-5 is designed to simulate the effects of sustained vigorous exercise, which otherwise may not be feasible for patients with MCI/AD.

Renew™ NCP-5, an External Counterpulsation (ECP) device, has a well-established safety profile and may increase cerebral perfusion that could be beneficial in the treatment of MCI due to AD and mild

---

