## 1.2 Renew™ NCP-5

Renew™ NCP-5, an ECP device, is a non-invasive treatment that improves coronary and peripheral vascular health and may improve cerebral vascular health. It enhances circulation and stimulates endothelial production of trophic factors such as nitric oxide, resulting in peripheral vasodilation, reduction in vascular inflammation and improved vascular compliance. These and other factors result in increased coronary artery blood flow, reduced cardiac afterload and reduced systemic blood pressure. Thus, Renew™ NCP-5 has been used to treat patients with chronic angina and Congestive Heart Failure (CHF) by increasing cardiac output and reducing the workload of the heart. ECP increases cardiac output by improving systolic unloading and venous return (Barsness, 2001). Patients with CHF have an increased risk of cognitive dysfunction presumably because of decreased CBF. In a study done by Kozdag, Iseri, et al. (2013), ECP therapy resulted in improvement in all cognitive domains except visual and verbal memory tests in patients with CHF. Thus, Renew™ NCP-5 may be used as an exercise alternative to increase CBF. The effects of Renew™ NCP-5 may act similarly to exercise therapy and are explored for patients with mild AD and MCI in this study.

Counterpulsation is a term that describes balloon inflation, when internal, or synchronized pressure during diastole and deflation in early systole, when external. During the Renew™ NCP-5 session, the patient's lower extremities are wrapped in three compressive pneumatic cuffs applied to the calves, lower thighs, and buttocks. Electrocardiogram (ECG)-gated, sequential leg compression occurs as these cuffs are inflated from distal to proximal in early diastole and then rapidly deflated at the onset of systole. The rapid inflation increases diastolic pressure (diastolic augmentation), increasing coronary perfusion pressure and myocardial perfusion. The rapid cuff deflation promotes lower extremity arterial "runoff" and leads to a decrease in systolic pressure (systolic unloading), thereby reducing cardiac afterload. The Renew™ NCP-5 session also increases venous return, promoting an increase in cardiac output.

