#### Confidentiality Statement

---

The confidential information in this document is provided to you as an investigator or consultant for review by you, your staff, and the applicable Institutional Review Board. Your acceptance of this document constitutes agreement that you will not disclose the information contained herein to others without written authorization from the sponsor.

The vADAS-Cog represents a collection of tests of different domains of brain function.

**A 2-point average change from baseline in vADAS-Cog at 12, 18 and 24 weeks after initiation of treatment will be used to determine effectiveness.** Examples of the typical functional changes associated with a 2-point change in vADAS-Cog include:

- Improvement in orientation – subject can now remember current date and day of week;
- Less errors in naming – 50% reduction in mistakes naming a real object;
- Improvement in following commands – subjects fail to follow 1/5 simple commands instead of 3/5 commands previously failed;
- Improvements in spoken language – misunderstanding decreases from moderately severe to mild (3-5 errors mean mild);
- Better constructional praxis – 40% improvement in number of figures copied correctly;
- Better word recall – 20% improvement in ability to remember words immediately after hearing them 3 times.

It is expected that the effect of the treatment will be demonstrated first at 12 weeks but will maintain or improve through to 24 weeks of treatment. Accordingly, since the 12 week (the completion of initial phase of treatment), 18 week and 24 week (end of maintenance phase) vADAS-Cog scores represent the entire expected period of the treatment duration, it is appropriate to measure the average of 12, 18 and 24 week vADAS-Cog scores as the primary endpoint for this study. The primary endpoint is the average of the change assessed at each of these three time points, referred to as an integrated primary endpoint.

Sponsor will repeat the analysis of the primary endpoint using 9-month and 12-month data.

As described in the Adaptive Design Report (ADR), included in Appendix A, the primary endpoint will be evaluated during interim analyses (after 100 subjects have been randomized and after every additional 25 subjects are randomized), up to a total of 250 subjects.

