  23. Current use of medications that in the investigator's judgement are incompatible with the study goals
  24. Significant changes in existing medical plans for treatment of cognitive impairment or dementia in last three months and/or or planned changes during the trial
  25. Presence of any of the contraindications for using the Renew™ NCP-5 device
  26. Athletic injuries, including Charley horses, pulled muscles and/or edematous muscles; necrotizing cellulitis in the past 30 days which would prevent the ability to perform the Renew™ NCP-5 treatment (evaluate and treat prior to Renew™ NCP-5 treatment)
  27. Unwilling or unable to maintain stable exercise regimen throughout the trial
  28. Participation in any clinical drug trial 30 days or five half-lives, whichever is longer, prior to screening visit

---

Confidentiality Statement

---

The confidential information in this document is provided to you as an investigator or consultant for review by you, your staff, and the applicable Institutional Review Board. Your acceptance of this document constitutes agreement that you will not disclose the information contained herein to others without written authorization from the sponsor.

29. Use of any device to increase cerebral blood flow in the past 30 days
30. History of claustrophobia
31. Subject unable to lay supine for 90 minutes

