## 7.5 Dosing and Administration

The subject is positioned lying flat on the foldable treatment bed and pneumatic, blood pressure like cuffs, are placed on his/her legs: calf, lower thigh and buttocks. They are connected to monitors that record heart rate and rhythm. The cuffs will be inflated and deflated based on the actions of the subject's heart (between heartbeats). Compression pressure will be given at different levels depending on whether the subject is assigned to the treatment group or the active sham group. The subject's overall ability to tolerate the treatment may impact the pressure applied. The operator of the device will increase pressure progressively and assess the subject's level of discomfort.

For all treatment subjects, the first four sessions represent the escalation phase. There will be a 5-minute ramp up period where the pressure is increased 1PSI / min until the desired pressure is reached. The goal for the treatment group will be at least 2.5 PSI (pounds per square inch) for the first treatment, and then escalate the pressure gradually through the fourth session at which time the goal for the subject should be at least an average of 3 PSI/session. For all sessions, the subject should reach the highest tolerable pressure. Patients are not to be terminated if they can't reach 3-6 PSI. Each treatment session is 60 minutes however, if necessary, on an as-needed basis, a treatment session of 30 minutes or more ( $\geq 30$  minutes) will be considered as a completed session.

After the fourth session, the operator shall continue to slowly increase the pressure to give the subject time to adapt to the rising pressure in order to reach the maximum level that the subject finds comfortable with a goal of reaching 3-6 PSI or the highest tolerable pressure. The operator may alter the pressure in the event that a subject becomes uncomfortable after the start of treatment. For both treatment arms, the Renew™ NCP-5 operator should record the average compression pressure and

---

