### Confidentiality Statement

---

The confidential information in this document is provided to you as an investigator or consultant for review by you, your staff, and the applicable Institutional Review Board. Your acceptance of this document constitutes agreement that you will not disclose the information contained herein to others without written authorization from the sponsor.

maximum diastolic augmentation (the ratio of diastolic peak height to systolic peak height – P/P) during each treatment session just before (1-2 minutes) reducing the pressure at the end of treatment.

Active sham control subjects will receive the same initial and maintenance treatment regimens as treated subjects except that the pressure will not exceed an average of 0.5 PSI over all treatments. Active sham subjects will undergo cognitive testing and imaging at the same time points as treated subjects. The purpose of the active sham Renew™ NCP-5 treatments is to give the subject an experience that seems to be an authentic treatment but, instead, provides minimal or no therapeutic benefit.

For a active sham treatment, the subject is handled exactly as in a typical therapeutic treatment (vitals, wrapping of cuffs, etc.), but with two important differences:

- The treatment pressure is set to a maximum of 0.5 psi and is kept there for the duration of the active sham treatment. Note that it may be difficult to maintain the pressure at exactly 0.5 psi. Although all attempts should be made to use a maximum of 0.5 psi, occasional, transient excursions as high as 1.0 psi are permissible.
- Although the subject will have ECG electrodes attached to his/her chest as per usual Renew™ NCP-5 protocol, the cable from those leads will not be connected to the Renew™ NCP-5 machine. Instead, the Renew™ NCP-5 machine will be connected to an ECG simulator hidden under the plastic “skirt” of the machine.

The ECG simulator is used to drive the Renew™ NCP-5 machine, rather than the subject’s actual ECG. This causes the "squeezes" applied by the machine to be out of sync with the patient’s heartbeat, thus minimizing any possible therapeutic effect.

ECG simulator settings are as follows:

- Normal sinus rhythm (NSR)
- Heart rate = 70 bpm
- Amplitude – 4 mV
- Sleep – No

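### Exclusion item 29 looks back only 30 days and does not name external counterpulsation, so a subject with earlier full-pressure treatment can enter and may recognise the sham

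*Protocol*

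**What the plan says.** Among the 31 exclusion criteria in Protocol section 6.2, item 29 is the only one aimed at earlier device use. It bars "Use of any device to increase cerebral blood flow in the past 30 days" and does not mention ECP by name. The nearby criteria do different work:

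- Item 24 excludes "Significant changes in existing medical plans for treatment of cognitive impairment or dementia in last three months", and planned changes during the trial.
- Item 25 concerns contraindications to the device.
- Item 28 excludes "Participation in any clinical drug trial 30 days or five half-lives, whichever is longer, prior to screening visit". It says nothing about device trials.
- Item 12 excludes current congestive heart failure. No item excludes stable angina.

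Section 7.5 says that the purpose of the sham "is to give the subject an experience that seems to be an authentic treatment". Sham pressure is set to at most 0.5 PSI, with occasional brief excursions to 1.0 allowed, and the cuffs follow an ECG simulator instead of the subject's own heartbeat. In the treatment arm the goal is at least 2.5 PSI in the first session and an average of at least 3 PSI by the fourth. Pressure then continues to rise "with a goal of reaching 3-6 PSI or the highest tolerable pressure".

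Under section 9.4 only the subject and the psychometrician are blinded. The device operator and the principal investigator are not.

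**The concern.** The sham has to convince. A subject who has never had ECP has nothing to compare it with. A subject who has completed a course at treatment pressure does, and may infer the assigned arm early on.

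With operator and investigator already unblinded, subject blinding is one of only two safeguards. Knowledge of the arm can affect effort on the vADAS-Cog, which is a performance test. It can affect the patient self-evaluation questionnaire. It can also reach the ADCS-CGIC, which takes patient and caregiver impressions, and the ADCS-ADL, which is a caregiver interview. Because recognition carries different information in the two arms, randomisation does not remove the resulting bias.

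A second, lesser worry is that a residual effect of an earlier course could shift the baseline of an exposed subject and shrink what further treatment can add.

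**Working it through.** The plan states no figure on this point, so there is none to reproduce. The check has four steps.

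**1. Who can enter.**

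| Earlier ECP | Item 24 | Item 29 | Result |
|---|---|---|---|
| For cognition, within 30 days | may apply | applies if ECP counts as such a device | probably excluded |
| For cognition, 30 days to three months ago | may apply | does not apply | possibly excluded |
| For angina, within 30 days | does not apply | applies if ECP counts as such a device | probably excluded |
| For angina, more than 30 days ago | does not apply | does not apply | can enter |
| For any purpose, more than three months ago | does not apply | does not apply | can enter |

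Such candidates can exist. The device is FDA cleared (section 7.1) and has been used for chronic angina and heart failure (section 1.2). ECP has been tried in small studies of Alzheimer-type dementia and MCI (section 1.4). Randomisation also has a high/very high cardiovascular risk stratum (section 5.1).

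**2. Contrast between the arms** (pressures from section 7.5).

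- First session: 2.5 / 0.5 = 5-fold.
- Later sessions: 3 / 0.5 = 6-fold to 6 / 0.5 = 12-fold.
- Against a transient sham excursion to 1.0 PSI: 2.5 / 1.0 = 2.5-fold in the first session, 3 / 1.0 = 3-fold at the lower later goal.

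These ratios describe the cue available to an experienced subject. They are not a measure of bias.

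**3. Possible size.** The documents give no frequency of prior ECP, so the share f is an assumption, applied equally to both arms of the maximum 250 subjects (section 6.3). Two effects are considered separately, against the 2-point vADAS-Cog criterion in section 5.2.1:

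- Carry-over: if exposed subjects gain nothing further, the effect becomes 2 × (1 − f).
- Recognition: if expectancy moves the contrast among exposed subjects by e points, the overall shift is f × e. The range e = 1 to 3 is also assumed.

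| f | Subjects of 250 | 2 × (1 − f) | f × e, for e = 1 to 3 |
|---|---|---|---|
| 2% | 5 | 1.96 | 0.02 to 0.06 |
| 5% | 12.5 | 1.90 | 0.05 to 0.15 |
| 10% | 25 | 1.80 | 0.10 to 0.30 |
| 20% | 50 | 1.60 | 0.20 to 0.60 |

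**4. Timing.** Section 5.2.1 says: "Sponsor will repeat the analysis of the primary endpoint using 9-month and 12-month data". Those visits fall on Day 252 and Day 365, and the week 24 visit on Day 168. The gaps are 252 − 168 = 84 days and 365 − 168 = 197 days, or 84 / 30 = 2.8 and 197 / 30 = 6.6 times the 30-day look-back.

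**The case against.** The case for leaving the text alone has real substance.

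- **Item 29 may cover ECP within its 30 days whatever the indication.** A reader might infer that ECP for angina always falls outside it, because section 1.1 says only that the device "may increase cerebral perfusion that could be beneficial". But section 3 states as the study's assumption that the device raises cerebral blood flow, and section 8.5.1 applies an effect-based test to other treatments begun during the study. An investigator would more naturally count ECP as covered. This stands, and the gap is mainly ECP given more than 30 days earlier.
- **Item 24 narrows it further** for recent ECP given for cognition. This also stands. It would be wrong to say without qualification that anyone who finished ECP two months ago is eligible.
- **Recognition is not documented.** The protocol has no data on it and gives no pressures for earlier courses. Preparation is the same in both arms, and active pressure varies with tolerance. The primary outcome is given by a blinded psychometrician. That protects against rater bias but not against a change in the subject's own effort.
- **Few may be affected.** Current heart failure is excluded, and section 3.2 says subjects would not otherwise have access to the device, although that sits awkwardly with its cleared status.
- **Carry-over.** A reader might infer from the 197-day gap that a 30-day washout contradicts the design. It does not. Repeating an analysis at 9 and 12 months tests for persistence without assuming it, the primary endpoint is measured at weeks 12 to 24, and no carry-over duration is stated. Randomisation balances prior exposure in expectation, so carry-over would dilute the effect and not favour the device.
- **Drop-out of sham subjects.** Section 8.4.15 offers them active treatment in a follow-up study only after the 12-month visit, which is a reason to stay.
- **History is already taken.** Section 8.1 collects past treatments and procedures. That could reveal prior ECP, but nothing makes it disqualifying.

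**Conclusion.** The gap is real and modest. No criterion requires subjects to be ECP-naive. A candidate with full-pressure ECP for angina more than 30 days ago, or with any ECP longer ago than items 24 and 29 reach, can be randomised. Such a subject may recognise a sham whose maximum is one-fifth to one-twelfth of the active goal, which weakens the blind for effort-dependent and patient- or caregiver-informed outcomes.

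The documents do not show that recognition happens or how many subjects have had ECP. At an assumed 2-5% prior exposure, the shift from recognition is 0.02 to 0.15 points for an assumed expectancy effect of 1 to 3 points. Carry-over would take a 2-point effect to 1.96-1.90. Only at assumed shares of 10-20% do the figures become appreciable, and nothing in the protocol suggests shares that high. The documents do not support the claim that the blind is broken or that carry-over biases the trial. This is a cheap improvement: worth making because it costs little and protects the sham comparison.

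**What to change.** Reword section 6.2, item 29 to exclude any previous external counterpulsation treatment, for any indication and at any time, and keep the 30-day look-back for other devices intended to increase cerebral blood flow. Naming ECP also removes any doubt about whether it counts as such a device.

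In section 8.1, add an explicit question about prior ECP to the medical and treatment history that is already taken.

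The cost is one eligibility line, one history question and a few more screen failures among patients already treated with ECP. If prior ECP is as uncommon as seems likely, that number is small. Pressures, schedule and assessments are unchanged.

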### 6.3 Recruitment and Retention

The study will enroll 100-250 subjects. Up to 16 sites will enroll at least one subject, and up to two will be international sites. A maximum of 50 subjects will be enrolled at a single site. Subjects will participate in the study for up to 13 months (up to 28 days screening, 24 weeks treatment and 6 months follow-up) and the study will continue for approximately 36 months.

Subjects will be recruited from the clinics and outpatient practices of the investigators participating in the study, referrals from community-based practices and from recruitment efforts. Study staff will be trained in approaches to recruitment and will be provided with flyers and brochures with patient information. Announcements will be placed on relevant websites. Research staff will provide support and education to the family/caregivers and ensure they understand the study and its potential benefits. A pre-screening questionnaire may be used to identify potential subjects who will be invited for an in-person screening visit. Eligible subjects will be randomized at multiple sites into the study.

Ongoing contact with the subject and caregiver during the treatment phase will be maintained, as the subject will receive treatments up to five days per week. Missed appointments will be followed up by phone calls to understand reasons for missing the treatment and support will be provided in the form of transportation, or other needs. After the intense initial phase, the subjects will be seen less frequently, but the sites will maintain contact with the subject through mail, email, text message and phone calls as needed.

### 6.4 Withdrawal or Termination

After randomization, all treatment subjects will have an initial four treatments (which are part of the planned 35 treatments) in which the PSI will be gradually increased to maximum tolerability with the goal of reaching 3-6 PSI by the fifth treatment. Subjects are not to be terminated if they cannot reach 3-6 PSI. Each treatment session will last for 60-minutes and a treatment session 30 minutes or more ( $\geq 30$  minutes) will be considered as a completed session.

The investigator can decide to withdraw a subject if any clinical adverse event, laboratory abnormality, or other medical condition or situation occurs such that continued participation in the study would not be in the best interest of the subject. Further, if a subject meets an exclusion criterion that precludes further study participation, she/he will be withdrawn from the study.

---

#### Confidentiality Statement

---

The confidential information in this document is provided to you as an investigator or consultant for review by you, your staff, and the applicable Institutional Review Board. Your acceptance of this document constitutes agreement that you will not disclose the information contained herein to others without written authorization from the sponsor.

Subjects are free to withdraw consent and discontinue participation at any time. Their decision to do so will not affect their ability to receive medical care or lose any benefits to which they are otherwise entitled.

All withdrawn subjects will be encouraged to complete study assessments at 6, 12, 18, 24 weeks, 9 and 12 months/end of study assessments and final MRI. Safety follow up procedures to capture adverse events, SAE or unanticipated problems will be initiated.

If the study is temporarily suspended or terminated early, written notification documenting the reason for study suspension or termination will be provided by the terminating party. The PI will inform the IRB and sponsor and provide the reason for termination or suspension. Determination of unexpected or significant risks to subjects, demonstration of efficacy, insufficient compliance to protocol requirements, determination of futility or incomplete data are some of the potential reasons for termination or suspension of the study. Enrolled subjects will be followed up to week 24 if the trial is terminated early.

